We will target individuals in our healthcare system residing in Philadelphia with a negative baseline screening CT and an upcoming or missed follow-up screening CT. Participants will be divided into receiving clinic + community support vs routine clinic only (control) based on residential location. The intervention group, consisting of individuals residing in West Philadelphia, will receive the option of enrolling in the CSP for obtaining their recommended LDCT. Community members designated as CSP representatives will receive basic training about LCS, transportation vouchers and information regarding other support services. They will also provide feedback to inform an interactive approach to reevaluating the intervention throughout the course of the study. Primary analysis will measure the 12-month follow-up LDCT adherence rate difference between clinic + CSP group vs clinic only group and its association with CSP enrollment. Additional analyses will measure differences in follow-up LDCT utilization before vs after intervention and extent of enrollment in the CSP in the intervention group. Planning and evaluation of our program will be performed using the widely utilized RE-AIM framework with emphasis on measuring reach, effectiveness, and sustainability of our approach.

Hypothesis: A community support program to facilitate lung cancer screening appointments will improve adherence to yearly follow-up screening compared to routine care alone.

Detailed Research Plan

Significance and Rationale:

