- 1. Develop a community support program for lung cancer screening adherence
- 2. Measure the impact of the community support program in improving adherence to lung cancer screening follow-up

Innovation: This study leverages novel neighborhood-level data to design and evaluate a community-based intervention using a robust implementation science framework, RE-AIM. This design allows for measuring impact on a population level thereby overcoming a common limitation of community-based interventions²⁷. Our utilization of CBPR builds on a strong collaborative community partnership with an extensive track record of successful community-based events. Led by members of the study team, our department has collaborated with the Community of Compassion CDC community center in West Philadelphia over the past two academic years to offer 3 events to the surrounding community (see letter of committment). This would support a seamless

incorporation of CBPR, an approach that is strikingly absent from the radiology literature despite evidence of its effectiveness in reducing disparities in cancer health outcomes.

Preliminary Data: Using data from our NCI-funded Population-based Research to Optimize the Screening Process (PROSPR) Center, which assesses LCS outcomes in five diverse healthcare systems³¹, we observed low adherence rates to LCS recommendations (55% across five systems; 36% overall at Penn Medicine)³². Adherence is significantly lower in Black patients at Penn Medicine and varies by baseline Lung-RADS score (21%-70% in Black patients; 32%-88% in White patients). Additionally, adherence is lower among patients living in impoverished neighborhoods (44% vs 63% in highincome neighborhoods). Geospatial analysis for neighborhood-level data of the 349 and 1,328 Philadelphia residents who received LCS in 2020 and 2021 respectively was applied to support our

intervention at the planning district level (Figure 1). West and Southwest districts contained 28% and 19% of all patients respectively. For residents who received a LDCT in 2020 with a Lung-RADS 1 or 2 recommendation,

which accounted for 90% of all studies, adherence to a 12-month follow-up study in 2021 was 24%. Data collection from 2022 is still in progress so estimates from 2020 and 2021 were utilized.

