will allow for iterative changes that incorporate feedback from CSP representatives and foster an equitable research partnership. The radiology PN and CSP representatives will meet weekly to discuss day-to-day activities and hurdles and maintain an open line of communication for daily interactions. Time-sensitive issues will trigger consortium meetings separate from the scheduled monthly review meetings. The initial and monthly consortium meetings will be guided by the RE-AIM framework with emphasis on improving the reach, effectiveness, and maintenance of our interventions (Table 1). The meeting following the 6-month intervention period will be focused on future planning. The Mixed Methods Research Lab (MMRL), under the guidance of co-investigator [name], will provide technical support to facilitate and evaluate the equitable inclusion of the various stakeholder perspectives into the study design and interactive changes.

Table 1. Demonstrating the RE-AIM planning and evaluation metrics

RE-AIM components	Question answered	Metric	Future Planning
Reach	How many patients that were offered entry into the community support program engaged with the representative Reasons for non-participation in program.	Number of patients who chose community support / total number of patients who were offered it; demographic and geographic differences of patients reached vs. not reached	Identify potential reasons for patients not choosing community support Identify other possible forms of community support.
Effectiveness	Did addition of community support option lead to increased adherence to follow-up recommendation?	% Of patients who obtained yearly follow- up LDCT in intervention vs control groups % Of patients in intervention group who obtained yearly follow-up LDCT after intervention vs during a similar prior time frame	Identify and compare characteristics of adherent vs non-adherent patients Capture any unintended consequences of community support for LCS Capture additional barriers to LCS adherence
Maintenance (Sustainability)	If the lung cancer screening community support program is effective, how can it be sustained?	Measure actual cost of community support program	Explore options for additional funding including through grants and institutional support Explore institutional return on investment for increased lung cancer screening utilization through community support program

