Specific Aim 2. Measure the impact of the community support program in improving adherence to lung cancer screening follow-up.

A prospective study would be designed to measure the impact of the CSP on a population level by utilizing aggregated neighborhood level data. The database contains information of patients who received baseline LCS with individual level residential address geocoded to determine neighborhood level characteristics (see preliminary data). The West Philadelphia planning district will be chosen as the intervention group because it is within the catchment area of Penn Medicine, has the highest number of LCS patients and is one of the districts noted to have consistent high rates of smoking prevalence and lung cancer mortality. In addition, we have strong community partnerships in the region. The control group would be individuals residing in the adjacent Southwest Philadelphia planning district which has a similar Yost score - a composite index of socioeconomic status⁴¹. Patients will be stratified into those with upcoming or missed appointments with primary analysis focused on patients with upcoming appointments. Informed consent will be provided prior to patient inclusion in the CSP. All activities will be approved by our Institutional Review Board prior to study commencement

We will identify patients residing in West Philadelphia who underwent lung cancer screening in 2020-2022 with a Lung-RADS 1 or 2 result and have an upcoming or missed appointment in our healthcare system downtown hospitals. We will analyze the EHR and RIS data to identify dates of LDCT upcoming appointments over 6 consecutive months with plans for 6 monthly cycles of intervention (Figure 3). A trained radiology PN will contact patients two weeks prior to their upcoming appointment, provide descriptions of the CSP and offer participation. Patients who agree to participate in the CSP would be contacted by a community representative

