1 week and 1 day prior to their appointment to offer support based on their identified needs and the available resources. The CSP representatives will be provided transportation vouchers, educational material and resources for other social support and liaise with the radiology PN to report information from patient encounters including additional needs and patient plans to attend appointments. Patients with missed follow-up appointments who still receive care at Penn Medicine will be contacted by the radiology PN for inclusion in the CSP program. The CSP representative will offer appointment support and collaborate with the radiology PN to offer a rescheduled LDCT appointment to this group of study participants.

Recruitment and Sample: The eligibility criteria for study inclusion are 1) obtained LDCT in 2020-2022 with a Lung-RADS 1 or 2 result 2) upcoming or missed follow-up LDCT 3) residence in the city of Philadelphia. Preliminary data revealed that 1,328 individuals residing in Philadelphia received a LDCT in 2021, 90% of which are Lung-RADS 1 or 2. Assuming the same number of patients receive LCS in 2022 and follow-up LDCT scans are evenly distributed throughout the year, we anticipate that 598 individuals will have an **upcoming LDCT study** in the first 6 months of 2023 of which 167 (28%) in West and 114(19%) in Southwest planning district will be included in our primary analysis. For secondary analysis, patients residing in West Philadelphia (28%) with **missed appointments** (66%) following a Lung-RADS 1 or 2 recommendation on LDCT(90%) in 2020 and 2021 will be included, resulting in an additional 278 patients.

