Evaluation: Evaluation will be guided by the RE-AIM framework with focus on Reach, Effectiveness and Maintenance of our program (Table 1). Primary outcomes of the study include: 1) difference in obtaining the recommended follow-up LDCT screening study in patients with upcoming appointments between the intervention and control group 2) association between participation in the CSP and adherence to follow-up LDCT. An intention-to-treat approach will be used for our primary analysis to measure the effectiveness of the CSP and will be done 2 weeks after completion of the 6-month intervention period. Chi-squared test will be used to measure a difference in adherence to follow-up LDCT between groups. A logistic regression model will be used to determine the association between adherence and utilization of CSP while controlling for demographic, geographic and socioeconomic variables. Secondary outcomes include: 1) difference in follow-up LDCT utilization in the intervention group compared to a similar period prior to implementation of CSP 2) reach of the CSP (what percentage of participants who were offered it engaged with the CSP representative). Evaluation of reach of the CSP would include descriptive analysis to evaluate differences in characteristics

the CSP and those who did not. Secondary analysis will include patients with **upcoming and previously** missed appointments following a negative screening study from 2020-2022. Mcnemar's test will be used to measure a difference in follow-up LDCT utilization after the

intervention compared to a similar

between participants who utilized

Table 2. Deliverables and Timeline (assuming start date of 11/1/2022)			
Deliverable	Target		
	Completion		
IRB Approval	11/30/2022		
Identification of CSP Representatives	11/15/2022		
Establishment of Consortium	11/30/2022		
Development of Support Material: Education, Transportation etc	12/31/2022		
Initiation of the CSP	01/01/2023		
Completion of the CSP	06/30/2023		
Data and Feedback Analysis	07/31/2023		
Manuscript and Presentation Preparation	09/30/2023		
Develop Structure for Future City-wide CSP	10/31/2023		

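### Does the lack of a latest qualifying date for the follow-up LDCT, with analysis two weeks after the period ends, distort the adherence comparison?

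*Combined protocol and SAP*

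**What the plan says.** All places are in the combined protocol and SAP.

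- **Outcome.** The Abstract says: "Primary analysis will measure the 12-month follow-up LDCT adherence rate difference between clinic + CSP group vs clinic only group". Under Evaluation, the first primary outcome is the "difference in obtaining the recommended follow-up LDCT screening study in patients with upcoming appointments between the intervention and control group". Neither place gives a tolerance around 12 months or a last qualifying date.
- **Appointments.** Specific Aim 2 identifies "dates of LDCT upcoming appointments over 6 consecutive months with plans for 6 monthly cycles of intervention". Recruitment and Sample assumes that "follow-up LDCT scans are evenly distributed throughout the year" and expects 167 West and 114 Southwest patients.
- **Analysis date.** The primary analysis "will be done 2 weeks after completion of the 6-month intervention period". Table 2 runs the programme from 1 January to 30 June 2023, with analysis finished by 31 July 2023. Those dates assume a start on 1 November 2022.
- **Prior-period comparison (secondary).** Table 1 compares West patients who "obtained yearly follow-up LDCT after intervention vs during a similar prior time frame".
- **Rescheduling.** For patients with missed appointments, the community representative works with the navigator "to offer a rescheduled LDCT appointment to this group of study participants". The plan does not say whether a rescheduled scan counts in the upcoming-appointment stratum.
- **Historical figure.** Preliminary Data reports that "adherence to a 12-month follow-up study in 2021 was 24" per cent.

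**The concern.** The terms 12-month and yearly say when the scan is due, not how late it may be. Because the analysis date is fixed, no common window longer than 14 days has closed for every patient. If late scans count without limit, a January appointment has about six months more than a late-June one in which to be scored adherent, and the planned test takes no account of that.

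Two comparisons could suffer. West v Southwest would be distorted if delays or appointment dates differed by district, for example if the programme rebooked West patients more actively. The prior-period comparison would understate the programme if historical records were read with much longer follow-up. The historical adherence figure adds to the doubt: counted by calendar year, it could include scans from 0 to 364 days after the due date.

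**Working it through.** **1. The plan's own figures.** 1,328 × 0.90 / 2 = 597.6, and 28% and 19% of 598 give 167 and 114. For a 1-df chi-squared test with N = 281, W = 0.17 and two-sided alpha 0.05, the noncentrality is 281 × 0.17² = 8.12 and power is 81.3%, which agrees with the stated 80%.

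To put W on the percentage-point scale, W = √(ab) × (p₁ − p₀) / √(p̄(1 − p̄)), with a = 167/281, b = 114/281 and p̄ = a·p₁ + b·p₀. Taking p₀ = 24% (Preliminary Data, used here as an assumed control rate) gives p₁ = 40.4%, a difference of 16.4 points.

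**2. Observation time at the cut-off.** There are 181 appointment days from 1 January to 30 June 2023, and the cut-off is 30 June + 14 days = 14 July. Follow-up f runs from 14 to 194 days, median 104. If the first navigator contact is on 1 January, the first contacted appointment is 15 January and the maximum is 180 days.

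The full range applies only if there is no window at all. With a window, f is capped:

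| Window | Follow-up range | Dates not yet complete | Closes for last patient |
|---|---|---|---|
| 14 days | 14 | 0 of 181 | 14 July |
| 30 days | 14–30 | 16 of 181 (9%) | 30 July |
| 60 days | 14–60 | 46 of 181 (25%) | 29 August |
| 90 days | 14–90 | 76 of 181 (42%) | 28 September |

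**3. West v Southwest.** The cut-off is the same for both, so equal behaviour gives equal scored rates. For a distortion, assume eventual adherence A = 24% in both districts, 80% v 50% of those scans on the booked day, and the rest after an exponential delay of mean m = 30, 60 or 90 days. None of the delay inputs comes from the documents. The spurious difference is A × 0.30 × mean[exp(−f/m)]:

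- No window, cut at 14 July: mean[exp(−f/m)] = 0.105, 0.252, 0.371, giving 0.76, 1.81, 2.67 points.
- Fixed 90-day window for all: exp(−90/m) in place of the mean, giving 0.36, 1.61, 2.65 points.
- Fixed 180-day window: 0.02, 0.36, 0.97 points.

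The 90-day window equalises follow-up but barely moves the difference, because what drives it is speed of scanning. Part of such a gap could be a real programme effect.

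**4. Prior period.** Same model, half of eventual scans on the booked day in both periods, A = 24%:

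- No window, and a cohort one year earlier read at the same data pull (f + 365 = 379 to 559 days): spurious fall of 1.3, 3.0, 4.4 points.
- A window complete for the prior cohort but cut at 14 July for the current one: 0.08–0.13 points (30 days), 0.5–0.6 (60 days), 0.9–1.2 (90 days).
- Prior period read to the matching date, or one closed window in both: 0.

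Table 1 and Evaluation both call for a similar earlier period. The ordinary sense is comparable length and cut-off, which is the last case.

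**The case for a change.** The strongest point on the other side is that this is the main endpoint, and two analysts with the same records could count late or rebooked scans differently. That stands: the documents neither state nor exclude the booked-visit rule, and they word the outcome as the scan rather than the visit. The 14-day ceiling on a common window also stands, and it does not depend on Table 2's provisional dates. Within the cohort, unlimited counting would make late appointments look worse. With half scanned on the booked day and the same delays as above, scored adherence is 24.0/23.4/22.3% for first-month appointments and 19.2/16.5/15.2% for last-month ones.

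Less of the rest holds. The within-cohort difference falls on both districts alike. Rescheduling is described for the missed-appointment group, which is outside the primary analysis, and nothing says that routine care in Southwest does not rebook. The larger prior-period figures need a historical cohort followed for more than a year past its appointments, against the plan's wording. The calendar-year adherence figure is preliminary data, not a definition of the trial outcome, and the power statement does not use it.

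The booked-visit reading also has support. Contacts come two weeks, one week and one day before a dated appointment, rides are for the day of the scan, and missed visits form a separate stratum. A two-week analysis date fits that design.

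**Conclusion.** The gap is real, but the plan as written is not shown to give a wrong result. The primary contrast has a common cut-off. Any distortion needs a difference between districts that the documents do not report, and under a marked assumed difference it is 0.8 to 2.7 points against about 16.4. The secondary prior-period comparison is unaffected if the similar period is read to a matching date. The sizes rest on 24% eventual adherence, even accrual and assumed exponential delays; the common cut-off needs none of these.

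An analyst would sensibly fill the gap in either of two ways: count attendance at the booked visit, in which case the two-week date stands, or apply one short window from the original appointment in both districts and both periods. A 30-day window closes on 30 July on the provisional calendar, inside the 31 July analysis target. Windows of 90 or 180 days are defensible preferences, but they move the data pull by 76 or 166 days (90 − 14 and 180 − 14), and the 90-day one brings little gain. This is missing detail, not a reason to change the plan.

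### Primary outcome 1 compares two non-randomised districts, one per arm, by an unadjusted chi-squared test, so any existing West-Southwest difference in adherence is counted in the CSP estimate

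*Combined protocol and SAP*

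**What the plan says.** All references are to the combined protocol and SAP.

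- **Allocation** (Abstract): "Participants will be divided into receiving clinic + community support vs routine clinic only (control) based on residential location".
- **Control district** (Specific Aim 2): "The control group would be individuals residing in the adjacent Southwest Philadelphia planning district which has a similar Yost score". West was chosen for catchment, patient volume, smoking prevalence and lung cancer mortality, and for a further reason: "In addition, we have strong community partnerships in the region". Under Innovation, the department reports working with a community center "in West Philadelphia over the past two academic years to offer 3 events to the surrounding community".
- **Primary outcome 1** (Evaluation): follow-up scan obtained or not, West against Southwest, in patients with upcoming appointments, by intention to treat. "Chi-squared test will be used to measure a difference in adherence to follow-up LDCT between groups".
- **Primary outcome 2** (Evaluation): a logistic regression for "the association between adherence and utilization of CSP while controlling for demographic, geographic and socioeconomic variables".
- **Before-after comparison** (Table 1, Effectiveness): "Of patients in intervention group who obtained yearly follow-up LDCT after intervention vs during a similar prior time frame". Evaluation makes this secondary, names McNemar's test, and includes both upcoming and previously "missed appointments following a negative screening study from 2020-2022". Specific Aim 2 says patients are stratified by upcoming or missed appointment.
- **Power Considerations**: 281 patients (167 West, 114 Southwest), two-sided 5%, 80% power at W = 0.17 with one degree of freedom.

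**The concern.** With one district per arm and no randomisation, district and program cannot be told apart. A raw two-by-two comparison gives the CSP credit or blame for anything else that makes West and Southwest patients differ in returning for a scan. The plan itself treats patient characteristics as needing control, but only in the model for CSP use.

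Primary outcome 1 is the only planned intention-to-treat test of assigned district, and so the main evidence for the hypothesis that the program improves adherence over routine care. If West would have had higher adherence anyway, a positive result may be partly or wholly a district difference. If West would have been lower, a real CSP effect may be missed. A city-wide program is among the listed deliverables, so the reading of this contrast has consequences.

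**Working it through.** **1. The plan's own figures.** Recruitment and Sample: 1,328 × 0.90 / 2 = 598; 28% of that is 167 and 19% is 114, total 281. Non-centrality is N × W² = 281 × 0.17² = 8.12. A 1-df non-central chi-squared at two-sided 5% gives power 81.3%. The stated 80% is right.

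**2. What W = 0.17 means in points.** W = √(0.594 × 0.406) × d / √(p̄(1 − p̄)), where 0.594 = 167/281, 0.406 = 114/281 and p̄ is pooled adherence. Preliminary Data gives two base rates: 24% (Philadelphia residents scanned in 2020, Lung-RADS 1 or 2) and 36% (Penn Medicine overall). Neither is split by district. Solving for d:
- Southwest 24%: West 40.4%, d = 16.4 points
- Southwest 36%: West 53.3%, d = 17.3 points

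**3. Rejection rate of the chi-squared test.** For true adherence pW and pS, with d = pW − pS:
- s0 = √(p̄(1 − p̄)(1/167 + 1/114))
- s1 = √(pW(1 − pW)/167 + pS(1 − pS)/114)
- rejection = 1 − Φ((1.96·s0 − d)/s1) + Φ((−1.96·s0 − d)/s1)

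Example: pS = 0.24 and pW = 0.29 give p̄ = 0.2697, s0 = 0.0539, s1 = 0.0532. Then (1.96 × 0.0539 − 0.05)/0.0532 = 1.05, and rejection is about 15%.

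**4. No CSP effect, West already higher.** The gaps are assumptions, because the documents give none.

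| Assumed gap | Southwest 24% | Southwest 36% |
|---|---|---|
| 0 | 5% | 5% |
| 3 points | 8.5% | 7.9% |
| 5 points | 15% | 13% |
| 10 points | 43% | 38% |

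The nominal 5% doubles to 10% at a gap of 3.6 points (24% base) or 3.9 points (36% base).

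**5. True effect of W = 0.17, West starting lower.**

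| Assumed deficit | Southwest 24% | Southwest 36% |
|---|---|---|
| 0 | 82% | 82% |
| 3 points | 66% | 66% |
| 5 points | 53% | 53% |
| 10 points | 21% | 23% |

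The 82% differs slightly from 81.3% because this formula uses the unpooled standard error under the alternative.

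**6. Whether another planned analysis closes the gap.**
- *Logistic model.* It belongs to primary outcome 2, so covariate control is planned at primary level. But its exposure is CSP use, which patients choose and which is offered only in West. It does not estimate the assigned-district contrast, and the plan does not say whether Southwest patients enter it.
- *Before-after comparison.* It can warn of a stable gap, for instance if West exceeds Southwest but has not risen over its own past. With no control district it cannot separate a CSP effect from a time trend.

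**The case against.** The strongest reply is that no gap has been shown. The districts adjoin and have a similar Yost score, and restriction to Lung-RADS 1 or 2 removes a large source of variation in adherence. At a 3-point gap the false-positive rate is 8.5%, which is not dramatic. With one district per arm the limit lies in the design, and covariate adjustment cannot remove an unmeasured district effect. All of this stands. It limits the severity and the promise of the fix, but it does not make the unadjusted contrast a clean estimate of the CSP effect.

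A reader might also infer more than the documents support:
- *That West and Southwest are known to differ.* Preliminary Data reports adherence of 44% against 63% by neighborhood income, a 19-point gap. That is the dimension on which the two districts were chosen to be similar, so it is a poor guide to the gap between them.
- *That earlier outreach raised adherence in West.* The documents do not say whether the three events covered screening, or whether Southwest had any.
- *That the chi-squared is the only analysis using the control district.* Southwest patients may enter the logistic model. What is established is narrower: it is the only intention-to-treat test of assigned district.
- *That the before-after check is spoiled by mixing upcoming and missed patients.* Stratification is mentioned in Specific Aim 2, and separate reporting is a natural reading.
- *That the power figure is wrong.* It reproduces.

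**Conclusion.** The concern holds as an unprotected bias of unknown sign and size. Primary outcome 1 adds any existing district difference to the CSP effect, and no planned analysis adjusts the assigned-district contrast. The stated 80% power refers to a CSP effect only if the two districts would otherwise have had equal adherence, an assumption the plan does not state.

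The sizes above are illustrations. They rest on assumed gaps of 3 to 10 points, base rates of 24% and 36% that are not district-specific, and the planned 167 and 114 patients. They show that gaps of under 4 points are enough to double the nominal error rate. They do not show that such a gap exists. This should be fixed in the analysis plan, but it does not by itself invalidate the study.

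**What to change.** **1. Adjust the district contrast.** Estimate primary outcome 1 as the intention-to-treat West-Southwest contrast from a logistic regression with a few prespecified demographic and socioeconomic covariates from the set already planned. Leave out any geographic variable that stands in for arm. Report a standardised risk difference with 95% CI and show the chi-squared result beside it. Keep covariates few: expected adherent patients number about 67 (0.24 × 281) to 130 (0.36 × 114 + 0.533 × 167).

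*Cost.* If covariates explain a share R² of the variation in arm, the standard error grows by 1/√(1 − R²): 1.054 at 10% and 1.118 at 20% (both assumed). The difference detectable with 80% power moves from 15.9 to 16.8 or 17.9 points at 24%, and from 16.9 to 17.8 or 18.9 at 36%.

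**2. Show the prior period in both districts.** Report prior adherence in West and Southwest under the same eligibility and outcome definition. Add a district-by-period estimate with CI as supportive only. State that it assumes parallel trends, and cluster on patient where someone appears in both periods.

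*Cost.* One query on data already geocoded. The 2020-scan cohort is about 88 West and 60 Southwest (349 × 0.90 × 0.28 and × 0.19). The 2021-scan cohort is about 335 and 227 (from 1,328), but its follow-up depends on 2022 data still being collected. These counts treat every Lung-RADS 1 or 2 patient as eligible. With base rate b and prior counts m1 and m2, the detectable difference solves d = (1.96 + 0.8416) × √((b+d)(1−b−d)/167 + b(1−b)/114 + b(1−b)(1/m1 + 1/m2)). At b = 0.24 this is 25.4 points with 88/60 and 18.6 with 335/227, against 15.4 without the prior-period term. The periods are treated as independent. This imprecision is why the estimate should be supportive.

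**3. State the assumption and limit the claim.** Say under Power Considerations that the figure assumes no underlying district difference. Word the conclusion as a non-randomised, district-level association in all cases, whether or not the analyses agree.

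These changes reduce measured confounding and make the rest visible. They do not remove unmeasured district effects.
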